Appendix E represents the data collection documentation tool for all medications.

SVT and DVT rates will be calculated based on upper extremity proven diagnosis of SVT and/or DVT in symptomatic cases. Researchers will review all study subject records in EPIC and screen for all upper extremity venous Doppler examinations. Radiology interpretations will be reviewed for findings of consistent with thrombus. This review will occur thirty days post patient discharge.

Infection rate will be tracked using confirmed blood stream infection data from epidemiology. These are cases in which line sepsis or bacteremia is confirmed by positive blood cultures.

Cost difference between approaches will be tracked. Equipment costs and personnel costs will be tracked. Number and type of IV catheters inserted/attempted will be extracted from the medical record. Supply costs will be estimated based on number of IVs attempted. Median time to successful catheter placement will serve as a baseline for estimating time needed for future reinsertions. Time will be assigned a monetary value. We will also track the number of patients from each group that require a PICC or CVC as a rescue catheter.

Sample Size and Power Analysis:

For this randomly allocated two-groups experiment, the primary outcome is catheter survival. Sample size calculation is based on primary outcome: composite or all cause premature removal due to complication of the IV catheter. Based on literatures and a new published article immediately prior to study period, we estimate sample size using the median survival time 30 hours for the 4.78 cm standard IV option. 91 subjects per group for a total sample size of 182 subjects is the minimum recommendation assuming a 10% dropout rate. This calculation

achieves power of 80% to detect a hazard ratio of 0.63 or less for line failure of the 6.35 cm ultra long IV based on log-rank test.

Statistical Analysis:

Characteristics of enrolled and eligible patients will be summarized between two arms using means [standard deviations] and medians [interquartile ranges] compared by t-tests or Wilcoxon tests for continuous variables and frequencies (percentages) compared by chi-squared tests or Fisher's exact tests for categorical variables.

Survival analysis methods (Kaplan-Meier curves, the log-rank test for continuous failure times or logistic model for discrete failure times) will be used for analyzing times to IV failure with non-failure times treated as censored. Proportions of SVT, DVT and catheter infection rates will be reported separately for each arm. Nonparametric summaries and a Wilcoxon Rank sum test will be used for the cost data. To test the effect of catheter variables on survival, we will further use Cox proportional hazard regression models for time-to-event outcomes and logistic regression models for binary outcomes. P-values of less than 0.05 will be considered statistically significant. Analysis will be conducted using SAS 9.4.

Study Site:

William Beaumont Hospital, Royal Oak (RO) campus is the proposed site for the investigation. It is a 1,100 bed major academic and referral center with Level 1 adult trauma and Level 2 pediatric trauma status. A major teaching facility, Beaumont, Royal Oak has 55 residency and fellowship programs with 454 residents and fellows. Beaumont is the exclusive clinical partner for the Oakland University William Beaumont School of Medicine. The Beaumont Research Institute was established more than 30 year ago at Royal Oak and offers research support services to clinical investigators.

The Royal Oak (RO) Emergency Center (EC) has the resources available to complete this project. This site is a tertiary care, level I trauma center with an annual ED census greater than 130,000 visits. I collaborated with nursing leadership in 2015 and implemented an ancillary staff-training program for placing US-guided IVs. Nearly forty ancillary staff members are certified in this procedure. Further, weekly logs of IVs placed under US-guidance show that an average of 10 US-guided IVs are placed daily. The RO EC has 130,000 annual visits of which many patients have difficult access. We also have 11 portable US machines with high frequency linear transducers that are ideal for vascular imaging.

Beaumont Health is Michigan's largest health care system and is the most preferred for health care in the tri-county area, according to National Research Corporation survey data. A not-for-profit organization, it was formed in 2014 by Beaumont Health System, Botsford Hospital and Oakwood Healthcare to provide patients with the benefit of greater access to extraordinary, compassionate care, no matter where they live in Southeast Michigan. Beaumont Health has total net revenue of \$4.5 billion and consists of eight hospitals with 3,429 beds, 187 outpatient sites,

nearly 5,000 physicians, 38,000 employees and 3,500 volunteers. In 2017, Beaumont Health had 175,700 inpatient discharges, 17,800 births and 575,000 emergency visits.

Potential Impact:

Optimization of peripheral vascular care is a critical strategy to improve patient outcomes and reduce health care costs. Enhanced dwell times will lead to improved patient/staff satisfaction, decreased interruptions in care with shorter hospital length of stay, and decrease in complications such as thrombosis, bleeding, and infection. Over 2 billion IV catheters are used worldwide annually with less than one-third of catheters actually ending up in a patient. No other industry would accept this degree of failure in its most essential and necessary process to deliver care. In a study by Rickard et al in 2012, a patient required an average of 1.7 IV catheters per admission.¹⁵ With a cost of approximately \$35 per catheter for straightforward insertions, even a slight improvement in dwell time has the potential to save our health system millions of dollars.

References

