A variable that may alter the survival of US-guided IVs that has not been studied extensively is the length of catheter that resides in the vein. Currently the general accepted rule is that an "adequate" amount of the catheter should be in the vein to avoid failure of the catheter.¹¹⁻¹⁴ However, this recommendation is only anecdotal and there has been no study to verify or quantify it. Our preliminary data focused on defining this relationship. In our study, **100% of catheters failed** in which less than 30% of the catheter was placed within the vein and **no failures** in those IVs in which at least 65% of the catheter was in the vein. All catheters in this analysis were commonly available 4.78 cm IVs. A key challenge for inserters is that achieving this quantity of catheter length in vein is impractical at the recommended angle of insertion when considering deeper target vessels. For many institutions, including ours, the 4.78 option is the longest stocked IV catheter and catheter survival is negatively impacted.

Central Hypothesis/Objectives:

We hypothesize that using an Ultra Long IV (6.35 cm) catheter increases the likelihood of ensuring a higher quantity of the catheter in the vessel lumen and leads to improved catheter longevity.

Primary Objective: Compare the IV survival between the Ultra Long IV (UL IV) (6.35 cm/20G) and the Standard Long IV (SL IV) (4.78 cm/20G) placed under US-guidance.

Function is defined as ability of catheter to flush 5 mL without resistance with or without blood sampling.

Secondary/Tertiary Objective(s):

Determine catheter survival based on vein depth.

Determine optimal cutoff length of catheter in vein for best survival profile.

Determine catheter survival based on angle of insertion.

Quantify specific etiologies related to premature catheter failure comparing UL IV to the SL IV.

Quantify overall costs associated with placement of the UL IV compared to the SL IV.

Determine overall success of placement UL IV versus SL IV.

Determine first-stick success UL IV compared to SLIV.

Determine number of attempts and time to insertion comparing UL IV to SL IV.

Safety Endpoint(s):

Compare phlebitis and thrombosis complication rates between the Ultra Long IV and the Standard Long IV.

[figure not shown]
Compare infection rates for all catheters.

Study Design:

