If the catheter was identified to have any signs or symptoms of complications during follow-up assessment the date and time of observation of the complication will be documented in the data collection tool and the primary team will be notified of the complication. If the catheter was removed prior to the follow-up assessment then the IV removal time and the reason for removal will be obtained through chart review. For all catheters removed due to a complication, re-insertion attempt data will be tracked through the medical record in the nursing section for venous lines and need for reinsertion of the IV or escalation to a midline, PICC, or CVC will be noted. If the patient is discharged prior to the time of follow-up assessment then the time of discharge will be documented and the IV will be presumed functional until time of discharge unless otherwise noted in the chart.

The medication administration record will be queried for all medications given through each catheter. Vesicants/irritants that are generally given via central line or considered caustic to the vessel will be noted in both groups. Number of doses will be recorded. See Appendix D for full list of non-neoplastic vesicants/irritants.

Additional data gathered by research staff on follow-up evaluation includes: dwell time in days/hours, hospital length of stay, and number of peripheral IVs or rescue catheters for duration of stay.

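### The thrombosis and bloodstream-infection definitions are not tied to the study catheter: as written they would admit rescue-line clots and bacteremia present on arrival, a small bias for the first and dilution for the second.

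*Combined protocol and SAP*

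**What the plan says.** The Safety Endpoint(s) section sets a comparison of devices: "Compare phlebitis and thrombosis complication rates between the Ultra Long IV and the Standard Long IV", and "Compare infection rates for all catheters".

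The case definitions stand in the later paragraphs of Study Procedure (Follow-up Assessment):

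- Thrombosis: "SVT and DVT rates will be calculated based on upper extremity proven diagnosis of SVT and/or DVT in symptomatic cases". To find cases, staff "screen for all upper extremity venous Doppler examinations". On timing: "This review will occur thirty days post patient discharge".
- Infection: "Infection rate will be tracked using confirmed blood stream infection data from epidemiology", followed by "These are cases in which line sepsis or bacteremia is confirmed by positive blood cultures".

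The same section expects replacement lines after a complication: "need for reinsertion of the IV or escalation to a midline, PICC, or CVC will be noted". Statistical Analysis reports SVT, DVT and catheter infection proportions for each arm and adds no attribution rule.

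Appendix B records the side of the study catheter and marks the attempt sites. Appendix C has daily rows with a Doppler result code, a yes/no for laboratory-confirmed infection, removal time and reason, and type of replacement access. It has no field for the side or vein of a clot, the source of an infection, or infection already present at enrolment.

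**The concern.** The endpoint asks which catheter causes more complications. The definitions count events in patients, whatever device or prior illness produced them.

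Two kinds of unrelated event can enter:

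- **Rescue-line clots.** A patient whose study catheter fails may receive a midline, PICC or CVC. A symptomatic arm clot from that line meets the written definition. If the ultra-long catheter fails less often, as hypothesised, the standard arm receives more rescue lines and more of these clots. The error would favour the ultra-long catheter and could partly offset a true excess of thrombosis from a longer catheter in the vein.
- **Bacteremia on arrival.** Eligibility names hemodialysis and IV drug use, and neither the eligibility text nor Appendix A excludes existing infection, thrombosis or an indwelling line. A positive culture from the presenting illness meets the written definition.

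**Working it through.** The documents give no expected rate, power or sample size for SVT, DVT or infection, so there is no figure to reproduce. The check is a reading of the text, followed by two illustrations of size.

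**1. Conditions looked for.**

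| Condition | Thrombosis | Infection |
|---|---|---|
| Same limb or vein | none | not applicable |
| Onset after insertion | none | none |
| No other line as source | none | none (bacteremia qualifies without a line) |
| Not present on arrival | none | none |
| Symptomatic and proven | yes | positive culture |

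The Appendix C removal reasons include infection but neither thrombosis nor phlebitis, so a clot cannot be linked to the study catheter through that field.

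**2. Spurious thrombosis excess from rescue lines.**

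From the plan: hazard ratio 0.63 and 91 per arm (Sample Size and Power Analysis). Assumed: 10-40% of failures are escalated to a rescue line, and 3-10% of rescue lines clot.

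Under proportional hazards and equal follow-up, if a fraction S of standard catheters survives, S^0.63 of ultra-long catheters survive. The gap in first failures is S^0.63 − S.

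- At S = 0.50: 0.646 − 0.500 = 0.146, that is, failure of 50% against about 35%.
- The maximum is where 0.63 × S^(−0.37) = 1, so S = 0.287. The gap there is 0.455 − 0.287 = 0.168, or 16.8 points.

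Spurious excess = gap × escalation × clots per rescue line:

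- Low: 16.8 × 0.10 × 0.03 = 0.05 points, or 0.05 patients in 91.
- High: 16.8 × 0.40 × 0.10 = 0.67 points, or 0.6 patients in 91.

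One event in 91 is 1.1 points, so the whole range lies below one patient.

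On the ratio scale, suppose both catheters truly cause 1% thrombosis and failure is 50% against 35%. With 10% escalation and 2% clots per line, the observed rates are 1.10% and 1.07% (ratio 0.97). With 40% and 10% they are 2.98% and 2.40% (ratio 0.81).

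**3. Dilution from unrelated events equal in both arms.**

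Observed rate = 1 − (1 − p)(1 − b), with p the device-related rate and b the unrelated rate. All rates are assumed: p = 5% against 1%, b = 5%.

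- 1 − 0.95 × 0.95 = 9.75%
- 1 − 0.99 × 0.95 = 5.95%

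The ratio moves from 0.20 to 0.61. Power with 91 per arm at two-sided 0.05 falls from 0.35 to 0.16. With b = 2% or 10% the ratio is 0.43 or 0.75 and the power 0.23 or 0.11. Power is low even without dilution.

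**The case against.** The strongest reply is that the documents are silent on attribution; they do not state a rule to count these events. A reader might infer that rescue-line clots and bacteremia on arrival are deliberately charged to the study catheter. The text does not support that. The Doppler screen is a case-finding step, the definition is limited to symptomatic proven cases, and the thirty-day sentence dates the review without defining an event window. Statistical Analysis speaks of catheter infection rates, which suggests that device-related events were meant. All of this stands, and it is why the point concerns what the wording would admit.

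A reader might also infer a large bias, for example from a 20-point gap in rescue-line use. At the design hazard ratio, the gap in first failures cannot exceed 16.8 points even if every failure led to a rescue line, and Appendix C also lists ordinary and ultrasound-guided peripheral IVs as replacements. A stronger true effect or repeat failures would raise the figure.

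Or a reader might infer that bacteremia on arrival tilts the comparison. It precedes randomisation, so it is balanced in expectation. The epidemiology data may also already separate such cases; the documents do not say.

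Finally, counting all events by randomised arm is a legitimate comparison that includes downstream effects, and Potential Impact expects such benefits. That stands too, so the all-event count should stay. It does not by itself answer the question about catheters that the safety endpoint asks. Much of the data needed for attribution is already planned, which makes the repair cheap but does not put it into the case definition.

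**Conclusion.** The point holds in limited form. As written, the definitions would admit any symptomatic proven upper-extremity SVT or DVT found in the record review, and any culture-positive bacteremia, while the safety endpoint compares the two study catheters.

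For thrombosis, the spurious excess in the arm with more failures is about 0.05-0.7 points, below one patient in 91. This rests on the design hazard ratio, proportional hazards, equal follow-up, first failures only, and the assumed escalation and clot rates. For infection, the effect is dilution without direction; its size depends on a background rate that the documents do not give.

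These are safety proportions reported by arm. The primary survival analysis and the sample size do not depend on them. The change is still worth making because events of this kind may be few and the definition is cheap to repair.

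**What to change.** Keep the all-event count by randomised arm and add a study-catheter-related count.

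- **Thrombus:** first diagnosed after insertion, in the limb of study-catheter insertion or attempt, within one fixed window from insertion that is the same in both arms. Any window up to 30 days is covered by the planned review, because insertion precedes discharge. Do not end the count when another device is placed: that would shorten follow-up in the arm that fails more and lose study-catheter clots imaged later. Do not restrict it to the cannulated vein, which would drop clots at failed attempt sites. Flag clots in a vein that also held a later line, and show them in a sensitivity count.
- **Bacteremia:** first positive culture drawn after insertion, no positive culture at or before insertion, and no other documented source.
- **Forms:** add side, vein, date and source to Appendix C, taken from records already under review.
- **Classification:** where feasible, classify events without the arm shown.

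The cost is definition wording and a little more chart abstraction. The attributable count will hold fewer events than the all-event count, which is why both should be reported.

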Staff members are expected to attempt a minimum of 3 attempts before enlisting another provider for help. A functional IV is confirmed by extraction of 5 mL of nonpulsatile blood and low-resistance infusion of a 5 mL normal saline flush without evidence of extravasation. Other data variables collected include: inserter details, need for rescue inserter, patient pertinent medical history, vitals, age, sex, first-stick success, cannulation success or failure, vein diameter, catheter in vein longitudinal measurement, angle of insertion, number of venous access attempts, time of IV insertion, time to IV insertion, location of IV insertion, distance of IV insertion from the antecubital fossa, medications infused, ionic contrast injection for computed tomography. A venous access attempt is defined as each time the needle punctures the skin. Once the IV is secured, research staff will measure distance from the puncture or catheter insertion site to the antecubital fossa to quantify the site to antecubital measurement. See Appendix B for Data Collection Tool for insertion-related variables.

Follow-up Assessment

After initial assessment, the catheter will be assessed by the research team every 24 hours as long as the patient is hospitalized. At each follow up interval the researcher notes the date/time of evaluation and assesses for any signs and symptoms of complications and functionality of the device. A catheter is functional if the IV flushes without resistance. Catheters will be assessed daily for signs and symptoms of complications. See Appendix C for details regarding the assessment for functionality and complications. Any signs or symptoms of complications or lack of functionality will be reported to the patient's primary care team so that management of the IV catheter can be addressed.

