Appendix B: Insertion-Related Data

Research Staff completing form (signature/date): _____

Catheter Type (circle): Ultra Long IV Standard IV

	Depth (cm)	Diameter (cm)	# Attempts	Depth (cm)	Diameter (cm)	# Attempts
	1 st Venous Access point				2nd Venous Access point	
Inserter #1 ID:						
	1 st Venous Access point				2nd Venous Access point	
Inserter #2 ID:						

[figure not shown]
Minutes for procedure completion (time from needle to skin to dressing site): _____

Time at Completion of Insertion: _____

Initial EC Vitals: BP _____ HR _____

Gender: _____ Age: _____ BMI: _____

Location of Successful Cannulation
(Mark 1/2/3 for access attempts, circle successful site): Left Right

Insertion site distance from AC fossa (cm): _____

Disposition (Circle): Observation Regular Progressive ICU Discharge

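### Reinsertion staff time rests on the median time of successful placements, but a total cost needs the mean time over all insertion procedures

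*Combined protocol and SAP*

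**What the plan says.** The costing rules are in the cost paragraph that closes Study Procedure, just before Sample Size and Power Analysis. It names two components: "Equipment costs and personnel costs will be tracked".

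- **Supplies.** "Supply costs will be estimated based on number of IVs attempted". The count comes from the chart: "Number and type of IV catheters inserted/attempted will be extracted from the medical record".
- **Staff time.** "Median time to successful catheter placement will serve as a baseline for estimating time needed for future reinsertions", followed by "Time will be assigned a monetary value". No staff rate, formula or value in minutes is given.

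Under Follow-up Assessment, for catheters removed because of a complication, "re-insertion attempt data will be tracked through the medical record in the nursing section for venous lines". The duration of a reinsertion is not among the items collected. The only procedure-duration field on the forms is in Appendix B, for the index insertion: "Minutes for procedure completion (time from needle to skin to dressing site". Initial Assessment also lists time to insertion as a variable. The plan does not say which of the two supplies the median, or whether the clock starts at the first skin puncture or at the successful one.

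The objective served is the secondary/tertiary one on overall placement costs by arm. Statistical Analysis plans nonparametric summaries and a Wilcoxon rank sum test for cost.

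**The concern.** The objective is a total cost, and Potential Impact speaks of savings to the health system. A total is a count multiplied by a mean. A median describes the typical procedure and gives little weight to the long ones, which still consume paid staff time.

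The baseline is also conditioned on success. A procedure that ends without a catheter counts towards supplies, which are costed by attempts, but adds nothing to the time figure. Such procedures are probably a minority, since the Background cites success above 90% for ultrasound-guided placement, but they are likely to be among the longest.

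At stake is the size of the reported reinsertion staff cost in each arm, and so the reinsertion part of any saving claimed for the longer catheter.

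**Working it through.** **Plan's own figure.** There is none to reproduce. The documents give no mean, median, SD or staff rate for procedure time, so every size below rests on stated assumptions.

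**Step 1: the identity.** For R reinsertions, total staff time = R × mean. The plan's input gives R × median. The fraction recovered is median/mean, and the shortfall is 1 − median/mean.

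**Step 2: is right skew likely?** This is inferred from the design. Every procedure needs at least one puncture ("A venous access attempt is defined as each time the needle punctures the skin"). Initial Assessment expects at least three attempts before a colleague is called in, and it records the need for a rescue inserter. Appendix B has room for two inserters with two access points each. A floor at one puncture with a multi-puncture, second-inserter tail points to right skew. With left-skewed times the sign reverses: for an assumed Beta(5,2) shape, mean/median is 0.97, so the median would overstate slightly.

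**Step 3: size under assumed log-normal times.** Median/mean = exp(−σ²/2), where σ is the log-SD.

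| σ (assumed) | median/mean | shortfall in reinsertion time |
|---|---|---|
| 0.25 | exp(−0.03125) = 0.969 | 3% |
| 0.5 | exp(−0.125) = 0.882 | 12% |
| 0.75 | exp(−0.28125) = 0.755 | 25% |
| 1.0 | exp(−0.5) = 0.607 | 39% |

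**Step 4: multi-puncture procedures and procedures that never succeed.** Simulation with 250,000 procedures per scenario. Assumed inputs: success per puncture 0.5, 0.7 or 0.9; at most 3 or 6 punctures; log-normal time per puncture with log-SD 0.25, 0.5 or 0.75. The mean time over all procedures, divided by the median among successes, was:

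- 1.11 to 1.45 if the clock starts at the first puncture (shortfall 1 − 1/1.11 = 10% to 1 − 1/1.45 = 31%);
- 1.15 to 2.61 if it covers only the successful puncture (shortfall 1 − 1/1.15 = 13% to 1 − 1/2.61 = 62%).

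With the first-puncture clock, the part due to dropping unsuccessful procedures can be isolated. At success 0.5 per puncture, cap 3 and log-SD 0.25, counting them raises the ratio from 1.22 to 1.36. At success 0.9 it goes only from 1.10 to 1.11.

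**Step 5: the between-arm difference.** Suppose one pooled time value is used and the true mean time per reinsertion is the same in both arms. The reinsertion staff-cost difference is then (difference in counts) × time × rate, and it shrinks by the Step 3 fraction.

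The net cost difference also contains the index catheter price and index insertion time. In hypothetical units, let the longer catheter cost 8 more at the index insertion and truly save 6 in reinsertions: net 8 − 6 = +2. If the saving is understated by 25%, it becomes 6 × 0.75 = 4.5 and the net is 8 − 4.5 = +3.5, further from zero. With no index difference, a net of −6 becomes −4.5, nearer zero. Either direction is possible.

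**The case against.** - **The distribution is not documented.** A reader might infer that staff cost is certainly understated. That needs right skew, which the design makes likely but no data in the documents establish. At log-SD 0.25 the effect is only 3%. This objection stands as a limit on the claim.
- **Failed punctures may already be counted.** A reader might infer that all failed attempts are left out. If the Appendix B clock starts at the first puncture, failures before an eventual success are inside the recorded minutes. Only procedures that never succeed are clearly dropped.
- **The multiplier is not fixed.** The plan calls the median a baseline for estimating and gives no formula, so it does not say that each reinsertion is priced at exactly that value. If the baseline were multiplied by attempts, failed attempts would be charged. In the simulation this recovers 0.75 to 0.97 of true time with a successful-puncture median, or 0.82 to 1.48 with a whole-procedure median, so cost could even be overstated. Against this, the text ties the baseline to reinsertions and describes no adjustment.
- **The net difference need not move toward zero.** A reader might infer a bias toward no cost difference. Step 5 shows that this does not follow, and the plan does not say whether the median is pooled or arm-specific. With arm-specific medians, the direction also depends on the skew in each arm.
- **The planned test hardly changes.** If reinsertion staff cost is a count multiplied by a common constant, replacing a median by a mean leaves the ranks of that component unchanged. Ranks of total cost move only through the weight of staff time against supplies. This is correct for the Wilcoxon p-value, but the estimated cost still changes, and cost in money is what the objective asks for.

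**Conclusion.** The point holds in limited form. A median taken over successful placements is the wrong input for a total staff cost. It is also the only time input that the plan states for reinsertions. If times are right-skewed, reinsertion staff time is understated by about 3% to 39% for assumed log-normal times with log-SD 0.25 to 1.0. These percentages apply to reinsertion time only, not to all personnel cost or to the whole saving. The shortfall carries over to the reinsertion part of the between-arm difference if a pooled value is used and the true mean reinsertion time is equal across arms. The direction of bias in the net cost difference is not determined.

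The calculation also takes index insertion times to represent reinsertion times, as the plan itself does. Cost is a secondary/tertiary objective that Study Design labels exploratory, so the primary analysis and the sample size are untouched. This is a worthwhile improvement of low severity.

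**What to change.** In the cost paragraph, replace the median by the arithmetic mean minutes per insertion procedure. Define the time as running from the first needle-to-skin contact to the end of the procedure, over all index procedures, successful or not, and including rescue-inserter time. Pool it across arms and multiply it by the number of reinsertions, counted as procedures rather than skin punctures so that count and mean share a unit.

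In Statistical Analysis, add mean cost per patient by arm with a bootstrap 95% CI, beside the planned Wilcoxon test, which does not compare mean or total cost.

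The cost is a few sentences and a small additional analysis. The Appendix B minutes field must also be completed when cannulation fails, with a defined end time, because the dressing endpoint does not exist in that case; minutes not recorded then may not be recoverable. The form must also capture the rescue inserter's time. The mean is more sensitive to outlying times than the median, so extreme values should be checked against source.
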